Initial Assignment and Display of Exercises. When patients first log into the IBET site, they complete a brief set of measures, described above, to determine their initial exercise level. Next, patients may select the gender and ethnicity (Caucasian, African American, Asian or Hispanic) of the animated model that demonstrates the correct technique for performing each exercise. Each time patients log in to the system, a static version of their strengthening and stretching exercises is displayed. Patients can click on each exercise to view the animated version. These files use vector graphics and can be made extremely small, allowing for nearly instantaneous presentation of the animations even with slow Internet connections. Patients are also prescribed aerobic exercises, corresponding in intensity to the five levels of strengthening / stretching exercises. After completing each exercise session, patients are asked to record their performance of the exercises in the website.

Changing Exercise Levels. At the end of each session patients are also given the option to move to a harder or easier workout at the next session. When patients opt for exercise progression, they are prompted to complete another web-based version of the mSF-WOMAC. If patients' mSF-WOMAC scores are higher (worse) than previously, they are not advanced to the next level yet but are instead given a new exercise routine at their current level. If patients' mSF-WOMAC score is less than (better) or equal to their previous mSF-WOMAC score, they are allowed to progress within the exercise continuum. As patients progress to more difficult levels, their exercise routine may contain more difficult exercises, previously assigned exercises with increased weight, more sets or repetitions, or an increase in the number of exercises. If patients request an easier exercise routine at any point, they are first advised that slight increases in pain or discomfort are common when beginning an exercise program, and they may want to try icing and rest and then resume their current exercise program but consider reducing the frequency initially. However, participants may still choose to immediately receive a new exercise program at an easier level. In addition, if patients have difficulty with any particular exercises (e.g., it is painful or they cannot get into the required position), the system also provides an option to exchange that exercise for another within the same level.

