Pain Monitoring. Patients are also asked to report any increased pain as a result of their exercises. If patients record increased pain for three consecutive settings without requesting a lower exercise level, they are sent an email suggesting they consider trying an easier exercise level. If patients do not record having increased pain for two weeks and have not requested an increase in exercise level in that interval, they are sent an email suggesting they consider trying a more difficult level. *IBET Pilot Study Data*

Design. This was single group, pre- and post-training study to assess the acceptability, feasibility, and preliminary efficacy of the virtual exercise training website.

Participants and Procedures. Participants were 10 primary care physicians and 42 of their patients (approximately 4 per physician) who had been diagnosed with knee OA. Patients were identified by the primary care providers. Eligible patients were provided with an access code for the IBET site, along with written instructions for entry. Patients completed all baseline assessments within the IBET site and were assigned an exercise routine as described above. After eight weeks of access to the IBET site, patients were asked to complete an online post-intervention assessment.

Results. Participants' average age was 62 years (SD=9); half were female; 40% had less education than a 4-year college degree. Use of the website was high. On average participants logged into the website 5.87 times per week and reported completing exercises 4.7 times per week. Table 1 shows mean baseline and follow-up scores for key study measures. The mSF-WOMAC decreased by about 7 points, which is a

Table 1. Results of IBET for Knee OA Pilot Study									
Baseline	8-Week Follow-up	Test Statistics							

substantial		Mean	SD	Mean	SD	t -value	p -value	pr			
improvement and a	mSF-WOMAC	18.07	7.75	11.14	8.47	6.19	<.001	.70			
large effect size.	WHOQOL-Physical	65.55	16.53	70.52	14.53	-2.11	.041	.31			
The World Health	WHOQOL-Psychological	73.81	13.98	75.62	13.91	-1.09	.280	.17			
Organization Quality	Knee Self-Efficacy	16.10	4.62	18.67	5.93	-4.02	<.001	.53			
of Life (WHOQOL) ⁵¹	SD=standard deviation; pr = point-biserial partial regression coefficient as measure of effect										
OI LIIC (VVI ICQCL)	-iitle 44 11 00										

size with .14 small, .36 medium, and .51 large effect (Rosnow & Rosenthal, 2008).

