C.5.0 Internet-Based Exercise Training Program. Participants randomized to the IBET group will be provided with access to the website described in detail above (Section B.5.). They will be encouraged to access the system starting as soon as they are enrolled in the study and through the 12-month follow-up assessment. Participants will be able to access the website as often as they like and may log their exercise daily. If participants do not interact with the website for seven days, they will receive an email encouraging them to access the website, and most importantly to remain physically active. In accordance with current Department of Health and Human Services and other guidelines for physical activity among older adults 61, we will encourage participants to complete strengthening and stretching exercises, guided by the IBET website, at least three times per week. Because the strengthening exercises are relatively low intensity and based on experience with the pilot study, we do not believe there are safety concerns if participants choose to perform strengthening exercises more than three times per week. However, as described above, if participants do experience an increase in pain, they will be advised to rest and then reinitiate their exercise program, considering a reduced frequency initially. Also in accordance with physical activity guidelines, participants will be told that it is safe and appropriate to perform aerobic exercises daily, or as often as possible, guided by the recommendations on the IBET website for their current exercise level. An overall guiding principle is that participants will be encouraged to be as physically active as their abilities, health conditions, and pain allow.

Some of the strengthening exercises included in the IBET program involve ankle weights and resistance bands. Therefore we will provide participants with ankle weights that can be adjusted in 1-lb increments, up to 5 pounds, as well as two resistance bands of different tension levels. These materials were also provided to participants in the pilot testing of the IBET program.

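### As written, the two-week email in B.5.0 would suggest a harder exercise level to an IBET participant who stopped because of pain and logged nothing

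*Combined protocol and SAP*

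**What the plan says.** All references are to the combined protocol and SAP.

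- **Harder-level email (B.5.0, Pain Monitoring).** The trigger is: "If patients do not record having increased pain for two weeks and have not requested an increase in exercise level in that interval". The action is: "they are sent an email suggesting they consider trying a more difficult level".
- **When records are made (B.5.0, Initial Assignment and Display of Exercises).** "After completing each exercise session, patients are asked to record their performance of the exercises in the website".
- **Pain email (B.5.0, Pain Monitoring).** "If patients record increased pain for three consecutive settings without requesting a lower exercise level, they are sent an email"; that email proposes an easier level.
- **Rest advice (B.5.0, Changing Exercise Levels).** "If patients request an easier exercise routine at any point, they are first advised that slight increases in pain or discomfort are common". Advice to ice, rest and then resume, perhaps less often at first, comes with this.
- **Inactivity email (C.5.0).** "If participants do not interact with the website for seven days, they will receive an email encouraging them to access the website". It also urges them to remain active.
- **General commitments (C.5.0).** "as described above, if participants do experience an increase in pain, they will be advised to rest and then reinitiate their exercise program". More broadly, "participants will be encouraged to be as physically active as their abilities, health conditions, and pain allow".

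C.5.0 gives the IBET arm the website described in B.5.0, so these rules apply in the trial. C.5.0 also lists four enhancements to be made before the study begins. They cover frequency instructions, personalized feedback, a new routine at the same level, and reading level. None changes the pain or email rules.

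**The concern.** The harder-level rule treats silence as freedom from pain. Two quite different participants meet it: one who exercises comfortably for two weeks, and one who stopped because the knee hurt and has not been back to the site. For the second, a suggestion to try something harder is the wrong message.

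IBET participants have no scheduled therapist visits, whereas the standard PT arm has 3 to 8. The automated emails are therefore the main prompts the plan describes for someone who has gone quiet. The other safeguards (choosing an easier level, exchanging an exercise, contacting the therapist co-investigators) all need the participant to act. What is at stake is the appropriateness of a safety-related message, not the estimation of the treatment effect.

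**Working it through.** The plan states no figure to reproduce here. The check follows the written rules for one participant.

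**Inputs**
- Harder-level email: 14 days with no recorded increase in pain, and no request for a harder level (B.5.0).
- Pain email: three consecutive recorded increases (B.5.0).
- Rest advice as located in B.5.0: given when an easier routine is requested.
- Inactivity email: 7 days without interaction (C.5.0).
- Encouraged frequency of strengthening and stretching: at least 3 times a week (C.5.0).

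**Assumed participant.** The last site contact is a painful session on day 0. The participant requests no change of level, contacts no one and logs nothing afterwards.

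| Day | Rule | Result |
|---|---|---|
| 0 | An easier or harder workout is offered at the end of a session | Not taken up (assumption) |
| 7 | Inactivity email | Sent; no pain check is described |
| 0 to 14 | Pain email | Not triggered, as three consecutive pain records are not reached |
| 0 to 14 | Rest advice on request for an easier routine | Not triggered, as no request is made |
| 14 | Harder-level email | Both conditions met, so sent |

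Sessions encouraged over the interval: at least 3 per week × 2 weeks = 6. Sessions logged: 0.

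Nothing in B.5.0 or C.5.0 says that the day-7 email suspends the day-14 email. If the participant abandoned the day-0 session and recorded nothing, the result by day 14 is the same, because the rule needs only the absence of a pain record.

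**What happens after the email.** If the participant then asks to progress, the site requires another mSF-WOMAC. A worse score keeps them at the current level; an equal or better score lets them advance. The check therefore limits actual escalation but does not correct the message sent.

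**The case against.** The strongest reply is that the rule is being read out of context. The Pain Monitoring paragraph begins with patients reporting increased pain that results from their exercises, so its author probably had in mind someone who is exercising without trouble. B.5.0 is a narrative summary, and the built site may already require use. This is plausible and limits the weight of the point. It does not remove it, because no such condition is written down. If the site works that way, one clause settles the matter.

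The traced case also needs several things to coincide. The participant must pass over the easier workout offered at the end of a session, not exchange the painful exercise, not contact the therapist co-investigators, and stay away for two weeks. That is fair. It makes the case less common but not impossible, since each of those options depends on the participant.

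A reader might go further and infer that the plan fails to give rest advice to participants in pain, because B.5.0 attaches that advice only to a request for an easier routine while C.5.0 refers back to it for any increase in pain. The documents do not support this as a defect. C.5.0 commits in its own right to advising rest when pain increases. The three-report email steers participants to an easier level, and requesting one brings the rest advice. The full email texts and the instructions given at assignment are not shown, so absence of the advice cannot be established.

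**Conclusion.** The point holds in a limited form. As written, the harder-level email can go to an IBET participant who stopped because of pain and logged nothing, a week after an email urging activity. This rests on the literal wording of B.5.0 and on the site working as described there.

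The size is small. The email only suggests, a worse mSF-WOMAC score blocks an advance, easier options are open throughout, and usual OA care continues. The placement algorithm also set levels slightly below those the therapists chose. The arm has 140 participants with access for 12 months, but how many would meet the rule in this way cannot be derived. The Human Subjects Protection section is not among these documents and may add safeguards.

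Two stronger conclusions might be inferred and are not supported. One is that the site moves people in pain to harder exercise automatically; it does not, because progression needs the participant's choice and the mSF-WOMAC check. The other is that the rule harms participants or biases the primary comparison; nothing in the documents shows either. This is a low-cost safety improvement to consider.

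**What to change.** 1. **Harder-level email (B.5.0).** Send it only if sessions were logged during the two weeks and none of them recorded increased pain. A workable condition is at least one logged session in each week: 1 × 2 = 2, against the 6 or more encouraged. If the site already does this, add the clause to B.5.0.
2. **Seven-day email (C.5.0).** If the last logged session before the seven days of inactivity recorded increased pain, include the existing B.5.0 advice (ice, rest, then resume) and the in-site route to the therapist co-investigators.
3. **Leave the C.5.0 sentence on rest advice unchanged.** It covers any increase in pain. Tying it to particular triggers would narrow a safeguard.

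**Cost.** One trigger condition and one email branch, which could join the enhancements already planned before the study starts. Those include charting log-ins and completed exercises, so the data for the first change should be available. The documents give no programming cost.

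**Downsides.** A participant who is well but does not log would get no harder-level email, although a harder workout is still offered at the end of each session. The therapist co-investigators may receive a few more questions. A participant who stops without ever recording pain would still get the standard seven-day email, but no longer the harder-level one.

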topics, collected as part of the baseline study assessments, will be provided to physical therapists, within the study database, for each participant. Physical therapists will also perform standard assessments including edema, range of motion, knee alignment, limb length equality, balance, and gait. The history and evaluation will be documented in the study database on a standard form, adapted from one we have successfully used in another study of PT for knee OA ⁵⁶. Based on these evaluations, therapists will provide treatment according to standard practice for knee OA, including: prescription of therapeutic exercise, balance / neuromuscular education, manual therapy, gait / stair training and advisement about shoes / wedges. Physical therapists may provide low-cost heel lifts or exercise therapy bands for patients when indicated. However, devices such as knee braces will not be provided. This reflects standard clinical practice, where patients typically pay out-of-pocket for devices such as knee braces and acquire them separately from the actual PT visit.

Education: Physical therapists may provide participants with basic education in activity pacing and joint protection strategies, as appropriate. Activity pacing involves recognizing typical pain patterns and activities that exacerbate pain, planning for activity during typical periods of low pain, planning for rest during typical periods of high pain, and taking rest periods when pain and soreness begin to occur. Joint projection strategies include decreasing the load on the knee joints during common activities such as walking, stair ascent / descent, rising from a chair, and doing other household activities. Participants may also be instructed in the use of heat, cold, elevation, and / or self-massage, particularly with reference to use in conjunction with home exercises.

C.7.0 Patient-Centered Outcome Measures

All study assessments will be conducted in person by a trained research assistant blinded to study group assignment. Primary and secondary outcomes, as well as process measures, will be assessed at baseline, 4-months, and 12-months. Demographic and clinical characteristics will be assessed at baseline. Participants will be paid \$30 for completion of assessments at each time point. We have selected our outcomes on the basis of the input from our Stakeholder Panel, as well as the Initiative on Methods, Measurement, and Pain Assessment in Clinical Trials (IMMPACT) ⁶⁶, which recommends measurement of four pain outcome domains: pain intensity (WOMAC pain subscale), physical functioning (WOMAC function scale, Satisfaction with Physical Function Scale, and Short Physical Performance Test Protocol), emotional functioning (Patient Health Questionnaire-8), and participant global impression of change. We have also included secondary outcomes and process measures related to physical activity.

C.7.1 Primary Outcomes: Western Ontario and McMasters Universities Osteoarthritis Index. The primary outcome measure for this study is the WOMAC, a measure of lower extremity pain (5 items), stiffness (2 items), and function (17 items). All items are rated on a Likert scale of 0 (no symptoms) to 4 (extreme symptoms). The reliability and validity of the WOMAC total score and subscales have been confirmed ⁶⁷. In patients with hip or knee OA, Bellamy et al. reported internal consistency coefficients (Cronbach's alpha) between 0.86 and 0.95 on WOMAC pain, stiffness, and function subscales. Construct validity has been confirmed by a significant association with the Lequesne Algofunctional Index for Knees ⁶⁷. The WOMAC has been widely used in trials behavioral interventions for patients with knee OA, confirming its sensitivity to change in these interventions.

C.7.2 Secondary Outcomes.

Satisfaction with Physical Function Scale. This is a validated 5-item questionnaire that assesses patients' satisfaction with their ability to complete basic functional tasks that are often affected by lower extremity OA, including stair-climbing, walking, doing housework (light and heavy, and lifting and carrying ⁶⁸. All items are rated on a 7 point scale ranging from Very Dissatisfied (-3) Very Satisfied (+3).

Objective Physical Function. We will objectively assess physical function using seven tests. This group of tests is relevant to the proposed study because they assess aspects of daily function that require lower extremity strength, and that are often impacted by knee or hip OA. This battery examines balance (4 tests including a side by side stand, semi-tandem stand, tandem stand, and a unilateral stand), time to rise from a chair and return to the seated position for 30 seconds, timed up and go-rising from a seated position, walking a short distance and returning to seated position, and a 2 minute step test. For each test, the possible range of scores is 0-4, for a total range of 0-20.

Depressive Symptoms – Patient Health Questionnaire-8. We have chosen to include depressive symptoms as a secondary outcome because of the close association of these symptoms with pain. Depressive symptoms

and severity will be assessed using the PHQ-8, a reliable and valid measure of depression⁷¹. The PHQ-8 is an eight-item survey derived from the Primary Care Evaluation of Mental Disorders (PRIME-MD) diagnostic tool, and consists of items corresponding to the depression criteria listed in the *Diagnostic and Statistics Manual Fourth Edition* (DSM-IV). Each of the eight questions is scored as 0 (not at all) to 3 (nearly every day), so that total scores range from 0 to 24.

The Knee injury and Osteoarthritis Outcome Score (KOOS). The KOOS is a patient-reported outcome measurement instrument, developed to assess the patient's opinion about their knee and associated problems. The KOOS evaluates both short-term and long-term consequences of knee injury and also consequences of primary osteoarthritis (OA) }. It holds 42 items in five separately scored subscales: KOOS Pain, KOOS Symptoms, Function in daily living (KOOS ADL), Function in Sport and Recreation (KOOS Sport/Rec), and knee-related Quality of Life (KOOS QOL). Some of these items overlap with those with the WOMAC, and in those instances questions will only be asked once.

The PROMIS Sleep-related Impairment Instrument. The PROMIS adult sleep related impairment item bank focuses on self-reported perceptions of alertness, sleepiness, and tiredness during usual waking hours, and the perceived functional impairments during wakefulness associated with sleep problems or impaired alertness. It assesses sleep-related impairment over the past seven days. This scale includes 8 items, each measured on a 5-point Likert scale.

The PROMIS Fatigue Instrument. The PROMIS Fatigue instruments evaluate a range of self-reported symptoms, from mild subjective feelings of tiredness to an overwhelming, debilitating, and sustained sense of exhaustion that likely decreases one's ability to execute daily activities and function normally in family or social roles. Fatigue is divided into the experience of fatigue (frequency, duration, and intensity) and the impact of fatigue on physical, mental, and social activities. It assesses fatigue over the past seven days, This scale includes 8 items, each measured on a 5-point Likert scale.

Patient Global Assessment of Change. We will use the Patient Global Impression of Change scale to evaluate participants' perspectives on overall changes in their joint pain during the study period. This single-item measure asks participants to describe their change in pain on a 7-point rating scale with the following options: "very much improved," "much improved," "minimally improved," "no change," "minimally worse," "much worse," and "very much worse." This scale has been widely used in clinical trials of chronic pain treatments and is specifically recommended by IMMPACT ⁶⁶.

The Brief Fear of Movement Scale. The Brief Fear of Movement Scale is a six item scale for assessing fear of movement in OA. The scale specifically assesses activity avoidance due to pain-related fear of movement. All items are measured on a 4-point scale from "strongly agree" to "strongly disagree." Physical Activity Measures

Physical Activity Scale for the Elderly. The Physical Activity Scale for the Elderly (PASE) is a self-report, 12-item scale that measures level occupational, household, and leisure activity during a one-week period. ⁷³ This scale was particularly developed for use among older adults; although all participants in the proposed study will not be age 65 or over, patients with knee OA typically have more limited physical activity than the general population. Therefore we believe this scale will be more applicable to our participant group than scales that were developed for younger adults.

Additional Self-Report Physical Activity Items. In addition to the assessment of overall physical activity that will be provided by the PASE, we are particularly interested in purposeful exercise behaviors that correspond to the IBET intervention and those typically prescribed in the context of standard PT for knee OA. We will ask participants, at each assessment point, to report the number of times and minutes per week, on average, they are completing strengthening, stretching, and aerobic exercises

Use of IBET Website / Number of PT Visits Attended. As described above, participants' use of the IBET website will be logged within the site. Therefore we will be able to compare use (e.g., number of log-ins and records of completion of exercise weekly) throughout the 12-month time period for participants in that study arm. Similarly, for patients in the Standard PT group, we will document the number of visits and the proportion of scheduled visits attended.

C.7.3 Process Measures. We will include two key process measures that have been associated with change in physical activity behavior. These will help us to understand potential mechanisms underlying any observed improvement in the IBET and / or standard PT interventions.

Self-Efficacy for Exercise Scale. The Self-Efficacy for Exercise scale assesses individuals' confidence in engaging in exercise in nine different situations that could present barriers (including having pain when exercising) ⁷⁵. For each situation, individuals are asked to rate their confidence in being able to exercise three times a week for 20 minutes each time, on a scale of 0 (not confident) to 10 (very confident). Validity of this measure was confirmed by expected associations with actual exercise, as well as physical and mental health. Social Support for Exercise Scale. ⁷⁶ This scale includes 13 items that assess the frequency with which friends and family members (separately) engage in behaviors that may either support exercise (e.g., "Gave me encouragement to stick with my exercise program") or discourage exercise (e.g., "Complained about the time I spend exercising"). All items are measured on a scale of 1 (none) to 5 (very often). The scale has shown acceptable test-retest reliability and internal consistency reliability. In addition, the scale was correlated with exercise habits, providing evidence of concurrent criterion-related validity ⁷⁶.

C.7.4 Demographic and Clinical Characteristics. For Specific Aim#3, we will focus on evaluating potential differential effects of the IBET and / or standard PT interventions, with particular interest in differences according to participant age and baseline physical function. We are interested in potential age-related differences for two reasons. First, we are interested in understanding whether older individuals respond differentially to an internet-based exercise program, since they may be less comfortable with this technology compared to younger adults. Second, older individuals typically have more comorbid health problems and activity limitations, and we are interested in understanding whether this results in any differential effectiveness of the two types of interventions. We are similarly interested in potential differences according to patients' baseline functional status, so that we can understand whether patients with more severe disease may respond differentially two the two types of interventions.

We may also explore differential effects according to some of the following additional participant characteristics, which are also important for describing the study sample: race / ethnicity, gender, household financial state, education level, work status, marital status, and internet use / comfort, health literacy, body mass index (BMI), joint involvement (i.e., report of all joints affected by arthritis), duration of OA symptoms, general self-rated health, and comorbid illnesses (Self-Administered Comorbidity Questionnaire ⁷⁸). C.7.5. OA Treatment Use. We will also assess participants' OA treatment use at each time point, via self-report, to evaluate whether there are any changes during the study period. For example, we are interested in understanding whether patients in the intervention groups may reduce pain medications if their symptoms improve. In addition, these data will provide information about whether other new treatment occurred (e.g., joint injection) that may have an impact on outcomes during the study period. Specific treatment aspects will include: pain medications for OA (prescription and non-prescription), knee braces, walking aids, physical therapy and joint injections. At the two follow-up time points we will also ask participants to indicate whether they think they currently use more, less, or about the same amount of pain medication to control their OA symptoms since starting the study.

C.7.6 Participant Feedback on IBET and Standard PT Arms. We will ask participants in the IBET group to complete the same Program Satisfaction questions described in the pilot study, at the 4-month assessment point. We will develop similar questions that pertain to the standard PT arm. In addition, we will ask participants to answer open-ended questions regarding both interventions. For example, we will ask participants which aspects of the interventions were most and least helpful, usability of the IBET website, content of the PT sessions, and ways we may be able to further improve the interventions.

C.8.0 Data Analyses

C.8.1 General Overview. Our statistical approach is guided by the PCORI Methods Report. For the superiority hypotheses (H1, H3), analyses will be conducted on an intent-to-treat (ITT) basis; patients will be analyzed in the arm to which they were randomized, regardless of adherence, using all data up to the 12-month follow-up or last available measurement prior to exclusion or dropout ⁷⁹. Additional exploratory analyses focusing on alternative, more restrictive analytic cohorts (e.g., as treated) may be considered for the superiority hypotheses, to provide additional information about the impact of magnitude of exposure to the interventions. For non-inferiority hypotheses (H2, H4), the ITT analysis would not be the conservative approach; therefore, it is recommended to perform analysis on both an intent-to-treat and per-protocol basis ^{80,81}.

C.8.2 Descriptive statistics. Descriptive statistics, including graphical displays, will be used to summarize all

study variables overall and by randomization arm. We will construct individual and mean trajectory plots of the

longitudinal outcome variables to understand their general trends over the study period. In addition, we will explore the variability and correlation structure of the longitudinal outcome variables. All statistical analyses will be performed using the SAS (Cary, NC) software package / R (www.r-project.org).

C.8.3 Missing Data. Because the main predictors of interest, intervention arm and patient characteristics, are collected at baseline, we do not anticipate much missing data in these variables. There may be missing values in the outcome measures due to dropout, death, a missed interim assessment, or item non-response. Given a thorough understanding of the missing data mechanism, it is possible to use all of the available information in analysis, rather than using only subjects with completely observed information. Our main analysis technique for the primary outcomes, general linear mixed models via maximum likelihood estimation, implicitly accommodates missingness when it is due either to treatment, to prior outcome, or to other baseline covariates included in the model, defined as missing at random 82. Therefore, inferences will be valid even if we have differential dropout by intervention arm. If the missing values are related to other measured patient factors, such as age or comorbidity, then multiple imputation (MI) provides a framework for incorporating information from these variables, while still preserving a parsimonious main treatment effect model 83, and is described as a significant advantage in recommendations from Panel on Handling Missing Data in Clinical Trials 84. Depending on the type and scope of missing data, MI will be conducted via the SAS procedure PROC MI or the SAS macro IVEware (http://www.isr.umich.edu/src/smp/ive/). If the probability of dropout is related to the actual missing response (which is unobserved because it is missing) or to other unobserved quantities, the missing data due to dropout is considered missing not at random (MNAR) or nonignorable 85. There is a possibility that data may be MNAR, and we propose as additional sensitivity analyses to explore MNAR methods, including selection and pattern-mixture models 85.

C.8.4. Specific Aim #1. H1 (Superiority): Patients who receive either IBET or standard PT will have clinically relevant improvements in pain, stiffness, and function, measured by the WOMAC at 4-month follow up, compared with patients in the WL control group; H2 (Non-Inferiority): The IBET intervention will be non-inferior to the standard PT intervention at 4-month follow-up, indicated by a mean WOMAC score less than 5 points higher than standard PT. For Specific Aim #1, we will use a linear mixed model (LMM) that accounts for the correlation between a participant's repeated measurements over time. Because of the small number of time points, we will apply an unstructured covariance matrix to take into account the within-patient correlation between repeated measures. The fixed-effect portion of the model will have the form: $Y_{it} = \beta_0 + \beta_1 4$ month+ β₂IBET*4month+ β₃PT*4month, where Y_{it} is the WOMAC score for subject i at t=0 and 4 months. We will estimate the parameters in the model and set up contrasts for tests of hypotheses using the SAS procedure MIXED (Cary, NC). Specifically, for H1, we will test for a difference in mean WOMAC scores between the IBET and/or PT group and the WL group at the primary time point of 4 months by testing that β_2 =0 and/or β_3 =0. For H2, we chose a non-inferiority limit of 5 points for mean WOMAC scores because it is reasonable and on the border of what would be considered a clinically important effect ⁸⁶. The null hypothesis in the non-inferiority framework is that IBET is inferior to standard PT in management of OA symptoms. We will test the noninferiority hypothesis by examining the estimate of the contrast β_2 - β_3 . Specifically, we will examine the 95% CI of the estimated contrast β_2 - β_3 , and if the upper limit of the interval is less than the threshold value of 5 points, we will conclude non-inferiority of IBET to PT 81. If we conclude non-inferiority, we test will for superiority of IBET to PT at 4 months by examining the 95% CI of the estimate of β_2 - β_3 for inclusion of 0 and the p-value for the test of the contrast β_2 - β_3 =0. Time is coded in this model to fit a constrained longitudinal data model (cLDA), in which baseline WOMAC score is modeled as a dependent variable in conjunction with the constraint of a common baseline mean across the treatment arms ⁸⁷. In this way, the cLDA model is comparable to an ANCOVA model; the two models are equivalent when there is no missing data. However, unlike an ANCOVA, participants who are missing follow-up measurements are included in the cLDA model because baseline is part of the response vector. For improvement in precision, the model will also be adjusted for enrollment site (stratification variable) 88. Similar procedures will be used to assess all continuous secondary outcomes. C.8.5. Specific Aim #2: H1 (Superiority): Patients who receive either IBET or standard PT will have clinically relevant improvements in pain, stiffness, and function, measured by the Western Ontario and McMasters Universities Osteoarthritis Index (WOMAC) at 12-month follow up, compared with patients in the WL control group; H2 (Non-Inferiority): The IBET intervention will be non-inferior to the standard PT intervention at 12month follow-up, indicated by a mean WOMAC score less than 5 points higher than standard PT. As

described above, will use a linear mixed model (LMM), adding in the 3 parameters for the 12-month period (12month, IBET*12month, PT*12month). We will follow the same testing procedures for the 12-month parameters as described for the 4-month. Similar procedures will be used to assess longer term effects of all continuous secondary outcomes at 12-months.

C.8.6. Specific Aim #3: Examine whether individual patient characteristics (particularly age and baseline functional status) are associated with differential improvement in the IBET and / or standard PT interventions. Patients may vary in their response to the intervention programs; this variation is known as heterogeneity of treatment effects (HTE). We will be conducting a descriptive HTE analyses 89. We have two a priori defined patient characteristics (noted above) and will conduct a separate descriptive HTE for each characteristic for primary and secondary outcomes, as defined in the PCORI Methods Report. We will initially treat age as a continuous variable and evaluate whether treatment response varies with increasing age; we will also evaluate treatment response within discrete age categories (e.g., by decade). With respect to functional status, we will evaluate potential differential response on the basis of participants' baseline scores on the SPPT (objective physical function test), since this is a separate measure from our primary outcome (WOMAC). We will initially treat baseline SPPT composite scores as a continuous variable (0-12). We will also evaluate treatment response within discrete baseline SPPT score categories of <5, 5-8, and >8, which have been shown to predict adverse outcomes. We will construct individual and mean trajectory plots of the longitudinal outcome variables by patient characteristics and treatment arm to understand their general trends over the study period. Our general steps in this secondary analysis will be to add the patient characteristics main effect, as well as the interaction variables, to the linear mixed model defined above. We will examine the parameter and 95% CI of the parameter estimates for the 3-way interactions treatment*time*patient characteristic (e.g. IBET*4month*age) to determine whether there is evidence of HTE for that characteristic. New state-of-the art modeling methods have taken the exploration of HTE to the next level, making it possible to explore and identify multidimensional subgroups exhibiting heterogeneous treatment effects. We will explore whether the a priori defined patient characteristics define multidimensional subgroups that exhibit HTE. We will utilize two different analytic strategies for doing so: multivariable logistic regression^{90,91} and recursive partitioning ^{92,93}. Each has unique strengths as well as limitations, and each approaches the problem of identifying the multidimensional subgroups differently. Our general steps in this secondary analysis will be: construction of outcome variables; identification of multidimensional subgroups via logistic regression and recursive partioning; and, finally, examination of treatment effects within the multidimensional subgroups.
